**Table 10-1 Outlier for Each Parameter in Laboratory Test**

Parameter (Unit)	Outlier Category
Hemoglobin (g/dL)	Decrease from baseline $\geq 1.5$ g/dL
Platelet count ( $10^3/\mu\text{L}$ )	Decrease from baseline $\geq 25\%$ and value $<$ LLN
	Increase from baseline $\geq 100\%$ and value $>$ ULN
White blood cell count ( $10^3/\mu\text{L}$ )	Decrease from baseline $\geq 50\%$ and value $<$ LLN
	Increase from baseline $\geq 20\%$ and value $>$ ULN
ALT (U/L)	Value $> 3 \times$ ULN
	Value $> 5 \times$ ULN
	Value $> 10 \times$ ULN
	Value $> 20 \times$ ULN
AST (U/L)	Value $> 3 \times$ ULN
	Value $> 5 \times$ ULN
	Value $> 10 \times$ ULN
	Value $> 20 \times$ ULN
AST (U/L) or ALT (U/L)	Value $> 3 \times$ ULN
	Value $> 5 \times$ ULN
	Value $> 10 \times$ ULN
	Value $> 20 \times$ ULN
Total bilirubin (mg/dL)	Value $> 2 \times$ ULN
	Increase from baseline $\geq 50\%$ and value $>$ ULN
PT-INR	Value $> 1.5$
BUN (mg/dL)	Increase from baseline $\geq 50\%$ and value $>$ ULN
Serum creatinine (mg/dL)	Increase from baseline $\geq 0.3$ mg/dL
ALP (U/L)	Increase from baseline $\geq 50\%$ and value $>$ ULN
AST (U/L) or ALT (U/L) + Total bilirubin (mg/dL) or PT-INR	(AST $> 3 \times$ ULN or ALT $> 3 \times$ ULN) and (Total bilirubin $> 2 \times$ ULN or PT-INR $> 1.5$ )

ALP = alkaline phosphatase; ALT = alanine transaminase; AST = aspartate transaminase; LLN = lower limit of normal; PT-INR = prothrombin time-international normalized ratio; ULN = upper limit of normal

All clinical laboratory summaries other than specialized tests will be based on the local laboratory measurements, and only the data that can be converted into standard units will be included in analysis. Summaries for specialized tests will be based on the central

laboratory measurements. Within the laboratory parameters, PTT will not be analyzed since during the study monitoring, study team found PTT was reported mixed with APTT.

All central clinical laboratory data and local clinical laboratory data will be listed. Values outside the normal ranges will be flagged for the central laboratory measurements.

### 10.3 Vital Sign Measurements

Summary statistics for vital sign measurements (systolic and diastolic blood pressure, pulse rate, respiratory rate, and body temperature) will be presented for baseline, EOT and TOC and for the changes from baseline to postbaseline.

Baseline vital sign measurements are defined as the last measurement obtained prior to the first infusion of the study drug. For postbaseline measurements, if multiple readings (ie, 3 readings) of vital signs are obtained in a day, the maximum body temperature within a study day and the associated systolic and diastolic blood pressure, pulse rate, and respiratory rate measured at the same time point will be used for the summary. If the multiple maximum body temperatures are obtained in a day, the first result among them will be used for the summary.

In addition, the number and percentage of subjects with the following prespecified outlier category (Table 10-2) during the postdosing period including unscheduled will be presented by treatment group.

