#### **7.5 Vital Signs**

Blood pressure (systolic/diastolic pressures), body temperature, pulse rate, and respiratory rate will be measured at Screening and at specified times.

The vital signs will be recorded once a day during Screening and at least 3 times a day at approximately evenly spaced intervals across the 24-hour day starting on Day 1 (calendar date) of the infusions and continuing while the patient is hospitalized and receiving treatment.

For patients treated in ICU, vital signs obtained through continuous monitoring methods, including intra-arterial catheters, may be used to record blood pressure, temperature, and heart rate.

The investigator or sub-investigator will consider whether changes from baseline are clinically significant (See also Section 7.12.6). Results of blood pressure, temperature, pulse rate, and respiratory rate will be entered in the eCRF.

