### **9.10.2 Vital Signs**

Vital signs measured at the time when highest body temperature is observed will be included in the analysis. Summary statistics for vital signs will be presented for EOT, TOC and for the change from baseline to each timepoint. Baseline will be the last value obtained before randomization.

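### EOT change in body temperature is biased upward, because baseline is a single last reading and the post-baseline value is taken at the day's highest temperature

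*SAP*

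**What the plan says.** SAP 10.3 summarises blood pressure, pulse, respiratory rate and temperature at baseline, EOT and TOC, together with the changes from baseline. Two different rules choose the reading.

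- Before treatment: "Baseline vital sign measurements are defined as the last measurement obtained prior to the first infusion of the study drug".
- After baseline: "For postbaseline measurements, if multiple readings (ie, 3 readings) of vital signs are obtained in a day", the summary uses "the maximum body temperature within a study day and the associated systolic and diastolic blood pressure, pulse rate, and respiratory rate" from that same time point.

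The second rule comes from Protocol 9.10.2: "Vital signs measured at the time when highest body temperature is observed will be included in the analysis". That section also fixes the comparator: "Baseline will be the last value obtained before randomization". The SAP moves this cut-off to the first infusion.

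Protocol 7.5 sets how many readings there are to choose from: "The vital signs will be recorded once a day during Screening and at least 3 times a day at approximately evenly spaced intervals" from Day 1, "continuing while the patient is hospitalized and receiving treatment". Protocol 8.3 lists vital signs at TOC without asking for repeats.

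For other data, SAP 6.3 takes the latest of several values on one day. SAP 10.3 overrides that rule only for vital signs after baseline.

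**The concern.** A change from baseline is interpretable when both ends are chosen in the same way. At EOT, the last day of treatment, the value is normally picked because it was the highest of several temperatures. The baseline value is picked only because it was the last. Subtracting one from the other adds a positive amount to the temperature change even in a patient whose temperature has not moved.

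Temperature should fall in this population as infection resolves, so the reported fall at EOT would be too small. Where TOC has one reading, the selection disappears and temperature appears to drop between EOT and TOC for no clinical reason. A reader could take this as continued improvement after treatment ended.

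**Working it through.** The documents give no SD, expected change or target for vital signs, so there is no planned figure to reproduce.

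**Inputs from the documents**
- Baseline: one reading, the last before the first infusion (SAP 10.3).
- EOT: k readings that day, with k at least 3 under Protocol 7.5. On a partial last day k could be 2.
- TOC: no required number; taken as k = 1.

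**Assumptions:** within-day temperature SD of 0.2 to 0.7 °C; readings independent and normal around the day's mean; within-day correlation r between temperature and each other sign, shown as a range.

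**Step 1: direction, with no distribution assumed.** A day's maximum is never below that day's last reading. Compared with a last-reading rule, the SAP rule can therefore only raise the EOT temperature or leave it unchanged. If three readings are exchangeable and untied, the last is the highest with probability 1/3, so the value is raised in about 2/3 of patients.

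**Step 2: size for temperature.** Bias = E[max of k standard normals] × SD, where E[max] = ∫ x · k · φ(x) · Φ(x)^(k−1) dx.

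| k | E[max], in SD | SD 0.2 °C | SD 0.3 °C | SD 0.5 °C | SD 0.7 °C |
|---|---|---|---|---|---|
| 1 | 0 | 0 | 0 | 0 | 0 |
| 2 | 0.564 | +0.11 | +0.17 | +0.28 | +0.39 |
| 3 | 0.846 | +0.17 | +0.25 | +0.42 | +0.59 |
| 4 | 1.029 | +0.21 | +0.31 | +0.51 | +0.72 |

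A simulation of 400,000 patients with no true change, SD 0.5 °C and k = 3 gave +0.42 °C under the SAP rule and 0.00 °C when last reading was compared with last reading. As an illustration at k = 3, a true fall of 1.0 °C would be reported as 1.0 − 0.17 = 0.83 °C at SD 0.2 °C, or 1.0 − 0.59 = 0.41 °C at SD 0.7 °C.

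**Step 3: EOT to TOC.** With k = 1 at TOC the bias there is 0, so the whole EOT bias reappears as a fall from EOT to TOC.

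**Step 4: the other signs.** They are carried along by the temperature choice, so bias = r × 0.846 × SD at k = 3.
- Pulse, SD 8 bpm, r 0.2 to 0.6: 0.2 × 0.846 × 8 = +1.4 to 0.6 × 0.846 × 8 = +4.1 bpm; zero if r = 0.
- Respiratory rate, SD 3/min, r 0.2 to 0.6: +0.5 to +1.5/min.
- Systolic pressure, SD 12 mmHg, r −0.3 to +0.3: −3.1 to +3.1 mmHg, so the sign is undetermined.

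**Step 5: between arms.** The bias cancels when the arms have the same k and SD. If the within-day SDs differ by 0.2 °C, 0.846 × 0.2 = 0.17 °C remains.

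**The case against.** The highest-temperature rule is a prespecified protocol choice, and a daily peak is a reasonable, cautious summary of fever. SAP 6.2 plans no test on vital signs, both arms are handled alike, and every reading is listed by subject. No safety conclusion is shown to rest on the mean EOT temperature change. All of this stands and keeps the point small. It justifies reporting a peak, but not subtracting a baseline chosen by another rule and calling the result change.

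The size is also open to challenge. The SD is assumed, three readings on the final day are not assured, and readings that are not independent would alter the factor. This too stands: the direction for temperature is secure, the amount is not.

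A reader might infer more than the documents support:
- **That every change column is invalid.** Where TOC has a single reading, it and baseline are both unselected, so that change is comparable.
- **That all vital signs are biased upward.** Selection is on temperature alone. The documents say nothing about how the other signs vary with it.
- **That the comparison of arms is compromised.** This would need different within-day variability or reading frequency between arms, and neither is documented.
- **That the outlier counts in SAP Table 10-2 inherit the bias.** Temperature is not in that table, and the text does not say whether the counts use the selected reading or all post-dose readings.

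**Conclusion.** The concern holds for EOT. Followed as written, SAP 10.3 biases the mean EOT change in body temperature upward. Under independent normal readings the bias is 0.56 within-day SD with two readings and 0.85 SD with three, or about +0.2 to +0.6 °C for three readings if the within-day SD is 0.2 to 0.7 °C. Pulse and respiratory rate probably move the same way to the extent that they track temperature; blood pressure could go either way. TOC change is little affected where there is one reading, so part of any fall in temperature from EOT to TOC may be an artefact.

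The damage is to change within each arm in a descriptive safety table. The difference between arms is largely preserved if within-day variability and reading frequency are similar. This is a minor correction, worth making because it is cheap.

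**What to change.** In SAP 10.3, compute change from baseline with one like-for-like rule:
- Baseline: the last reading before the first infusion, as now. The last reading of Day 1 would not do, because it may follow that infusion.
- EOT and TOC: the last reading of the visit day, under the latest-value rule of SAP 6.3.
- At each point, use the blood pressure, pulse and respiratory rate recorded with the chosen reading.

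Keep the daily maximum temperature of Protocol 9.10.2 as a separate post-baseline peak summary, without a change column. List the departure in SAP Section 15. The SAP's move of the vital-sign baseline from randomization to first infusion is not listed there either and can be added in the same edit.

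The cost is a few sentences and a different record-selection flag. Protocol 7.5 already has the results entered in the eCRF, and Protocol 9.1 allows departures that the SAP details and justifies. Two small downsides remain: the departure from Protocol 9.10.2 itself, and some mismatch in time of day between the baseline reading and the last reading of a visit day.

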**Table 10-2      Outlier for Each Parameter in Vital Sign Measurements**

Parameter (Unit)	Outlier Category
Systolic blood pressure (mm Hg)	Value $\geq$ 160 or increase from baseline $\geq$ 20
	Value $\leq$ 90 or decrease from baseline $\geq$ 20
Diastolic blood pressure (mm Hg)	Value $\geq$ 105 or increase from baseline $\geq$ 15
	Value $\leq$ 50 or decrease from baseline $\geq$ 15
Heart rate (beats per minute)	Value $\geq$ 120 or increase from baseline $\geq$ 15
	Value $\leq$ 50 or decrease from baseline $\geq$ 15

A listing of all vital sign measurements will be provided by subject.

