#### **4.4.3.4 Sepsis-specific Inclusion Criteria**

Patients who fulfill the following criteria at Screening will be included in the study:

1. Patients defined for SIRS (Appendix 2), indicated by having 2 or more of the following responses:
  - a. Oral or tympanic body temperature greater than 38°C (100.4°F) or less than 36°C (96.8°F)
  - b. Tachycardia, heart rate greater than 90 beats/minute
  - c. Tachypnea, manifested by a respiratory rate greater than 20 breaths/minute or hyperventilation, as indicated by an arterial partial pressure of carbon dioxide (PaCO2) of less than 32 mm Hg
  - d. WBC greater than 12,000 cells/mm^3, less than 4000 cells/mm^3, or > 10% immature (band) forms
2. Patients with an identified infection site from which a carbapenem-resistant Gram-negative pathogen has been isolated using an appropriate clinical specimen

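### SAP Table 10-2 joins the absolute limit and the change from baseline with *or*, so recovery and unchanged abnormal baselines are counted as vital-sign safety outliers

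*SAP*

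**What the plan says.** SAP Table 10-2 has six categories, a high and a low one for each of systolic pressure, diastolic pressure and heart rate. All six join the two conditions with *or*:

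- Systolic: "Value $\geq$ 160 or increase from baseline $\geq$ 20" and "Value $\leq$ 90 or decrease from baseline $\geq$ 20".
- Diastolic, high: "Value $\geq$ 105 or increase from baseline $\geq$ 15".
- Heart rate, high: "Value $\geq$ 120 or increase from baseline $\geq$ 15".
- Diastolic, low, and heart rate, low (same wording): "Value $\leq$ 50 or decrease from baseline $\geq$ 15".

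SAP Section 10.3 sets baseline as the last measurement before the first infusion. Subjects with a category "during the postdosing period including unscheduled will be presented by treatment group". For the by-visit summary the same section takes the reading at the day's highest temperature. It does not say whether that selection also governs the outlier count. Protocol Section 9.10.2 limits the vital-sign analysis to the reading at the highest temperature.

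In SAP Table 10-1, every laboratory row that pairs a change with a normal-range limit uses *and* (platelets, white cells, BUN, ALP, one bilirubin row). An example is "Decrease from baseline $\geq 25\%$ and value $<$ LLN". Haemoglobin and creatinine there use change alone, in the worsening direction only.

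**The concern.** Patients enter while acutely ill. For sepsis, "Tachycardia, heart rate greater than 90 beats/minute" is one of the qualifying responses (Protocol Section 4.4.3.4), and only refractory septic shock is excluded (Protocol Section 4.3), so other hypotension can be present at baseline. Successful treatment moves heart rate down and low blood pressure up. Under *or*, that movement alone places a patient in the same category as a heart rate of 50 or a systolic pressure of 160.

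Safety is the first-listed secondary objective (Protocol Section 2.2), and Table 10-2 is the SAP's only categorical vital-sign output by treatment group. If one arm recovers more often or faster, its low heart-rate and high blood-pressure counts go up for that reason, and a reader of the table cannot tell this from harm.

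**Working it through.** **Step 1. Apply the rules to single patients.** The plan states no outlier rate, so there is no figure to reproduce. The table compares the rule as written, the same limits joined by *and*, and a count of new crossings (post-dose value beyond the limit, baseline not beyond it).

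| Baseline to post-dose | Change | *or* (as written) | *and* | New crossing |
|---|---|---|---|---|
| Heart rate 112 to 90 | -22 | low outlier | no | no |
| Heart rate 95 to 85 | -10 | no | no | no |
| Systolic 92 to 115 | +23 | high outlier | no | no |
| Diastolic 45 to 70 | +25 | high outlier | no | no |
| Systolic 165 to 162 | -3 | high outlier | no | no |
| Systolic 105 to 86 | -19 | low outlier | **no** | **yes** |
| Heart rate 110 to 122 | +12 | high outlier | **no** | **yes** |

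Rows 1, 3 and 4 are recovery and row 5 is an unchanged abnormality; all four are flagged only under *or*. Row 2 shows that a small recovery is not flagged. The change must reach 15 beats/min, 20 mm Hg systolic or 15 mm Hg diastolic. The last two rows are new abnormalities that *and* loses.

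**Step 2. Illustrative size.** None of these inputs is in the documents; all are assumptions:

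- True heart rate at entry: mean 98, between-patient SD 14. True systolic: mean 120, SD 18.
- Within-patient SD: 6 or 8 beats/min, paired with 8 or 12 mm Hg.
- Recovery of -12 beats/min and +8 mm Hg, reached in equal steps by the last reading.
- 10 or 30 post-dose readings. One a day for 7 to 14 days gives 7 to 14. Three a day (Protocol Section 7.5) gives 3 x 7 = 21 to 3 x 14 = 42.

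Each observed value is the true value plus independent normal error, and baseline is one such reading. A patient counts if any post-dose reading meets the rule. With 20,000 simulated patients per scenario, the ranges over the four scenarios are:

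| Category | *or* | *and* | New crossing |
|---|---|---|---|
| Low heart rate, with recovery | 63-84% | 1-5% | 2-5% |
| Low heart rate, no recovery | 20-57% | about 1% or less | about 1% |
| High systolic, with recovery | 44-81% | 5-23% | 9-25% |

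**Step 3. What this could do to an arm comparison.** In matched scenarios, the low heart-rate flag is 27.5 to 44.4 points more common with recovery than without. If the share of recovering patients differed between arms by 20 points (an assumption), the flag rate would differ by 0.20 x 27.5 = 5.5 to 0.20 x 44.4 = 8.9 points, against the arm doing better.

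**Step 4. Cost of a blanket *and*.** In the same simulation, with and without recovery, *and* leaves about 21-84% of patients who newly reach systolic 90 or below unflagged. The reason is simple: anyone starting below 110 must fall below 90 before the 20 mm Hg change is met. With mean 120 and SD 18, that is P(Z < (110 - 120)/18) = P(Z < -0.56), about 29% of patients. Likewise P(Z > (105 - 98)/14) = P(Z > 0.5), about 31%, start above 105 and can pass a heart rate of 120 without a 15-beat rise.

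**The case against.** The case for leaving the table alone has real content.

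- **The table is a screen, not a test.** SAP Section 6.2 plans no inference on vital signs, high and low are separate rows, and no endpoint or decision depends on the count. This stands.
- **Other outputs exist.** SAP Section 10.3 gives change from baseline at EOT and TOC, all readings are listed by subject, and clinically significant changes are recorded as adverse events (Protocol Section 7.12.6). A reader might infer that a haemodynamic signal would be lost; with these outputs it would be diluted in this table, not hidden from the study.
- **The tachycardia criterion is narrow.** It is one of four SIRS responses, two are needed, and it applies to sepsis entry only. BSI/sepsis is planned at about 20% of patients (Protocol Section 3.2.1). This limits how far the entry criterion alone carries the argument. The mechanism does not depend on it, since every patient's baseline is taken during infection.
- **Table 10-1 is not a uniform template.** Some of its rows use change alone or a limit alone. A reader might infer that the SAP contradicts itself; it does not. Table 10-1 shows only that a stricter pairing is already in use.
- **A blanket *and* would do harm.** This is correct (Step 4) and shapes the fix.

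**Conclusion.** The point holds on the wording of the table. Recovery of the stated size and unchanged abnormal baselines are counted as safety outliers, and the low heart-rate and high blood-pressure counts rise as patients improve. This can make the more effective arm look less safe in that table.

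The size is uncertain. The percentages above rest on assumed means, SDs, recovery and numbers of readings. They show direction and rough scale only. A reader might infer that the table will mostly count recovery and noise, or that nearly every patient will be flagged; the documents contain no data to establish either.

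The effect is confined to a descriptive safety table, so this is something the sponsor should correct rather than a threat to the trial's conclusions.

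**What to change.** For each of the six categories in Table 10-2, replace the single *or* count with separate rows:

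1. Value beyond the absolute limit when baseline was not beyond it (new abnormality).
2. Value beyond the absolute limit and the stated change from baseline, matching the paired rows of Table 10-1. This also catches worsening from an already abnormal baseline, such as systolic 88 to 65 (a fall of 23).
3. If wanted, the change alone, labelled as a change and not as an outlier.

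Do not make row 2 the only count, because it misses new crossings such as systolic 105 to 86.

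State in SAP Section 10.3 whether the table uses all post-dose readings or only the reading at the day's highest temperature. If all readings are used, list this in SAP Section 15 as a change from Protocol Section 9.10.2. If only that one reading is used, say so, since low pressure at another time of day will not be counted.

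The cost is a few more table rows, a small program change and smaller outlier counts. A small worsening from an already abnormal baseline (systolic 88 to 80, a fall of 8) enters none of the three rows and would be seen only in the listing. No new data are needed.

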## 11. Pharmacokinetic Analyses

Individual plasma concentrations of cefiderocol will be listed and summarized by nominal sampling time window. Individual plasma concentrations of cefiderocol will also be summarized by nominal sampling time window and dosing group based on renal function (augmented renal function, normal renal function, mild renal impairment, moderate renal impairment, severe renal impairment, end-stage renal disease, subjects with intermittent hemodialysis, continuous venovenous hemofiltration, continuous venovenous hemodialysis, and continuous venovenous hemodiafiltration). The summary statistics will include the number of nonmissing observations (N), arithmetic mean (Mean), SD, and coefficient of variation (CV%, calculated by  $SD/Mean \times 100$ ),

geometric mean and coefficient of variation for geometric mean (CV% Geometric Mean), and median, minimum, and maximum values. The CV% Geometric Mean will be calculated according to a formula  $CV\% \text{ Geometric Mean} = [\exp (sd^2)-1]^{1/2} \times 100$ , where  $sd$  is the SD for natural log (ln)-transformed data. If the number of nonmissing observations at a time point is less than 3, the data at the time point will not be summarized.

Individual plasma concentrations, if deemed to be anomalous, may be excluded from the analysis at the discretion of the PK study director. Any such exclusion will be clearly listed in the study report along with justification for exclusion.

For the summary of plasma concentrations, plasma concentrations below the limit of quantification (BLQ) will be treated as 0 for calculations of Mean, SD, CV%, median, minimum, and maximum values and treated as missing for the calculation of geometric mean value and CV% Geometric Mean.

Population PK analyses will be planned and reported separately by the Clinical Pharmacology & Pharmacokinetics of Shionogi & Co., Ltd.

